The overall objective of this multicenter trial is to determine whether use of a low-cost, high-resolution microendoscope during diagnostic upper endoscopy can improve the efficiency and accuracy of endoscopic screening for esophageal squamous cell neoplasia (ESCN). This is a trial of a novel technology, a miniaturized, low cost (<\$3,500) microscope device which can be used during upper endoscopy to image the gastrointestinal epithelium. This portable, battery-operated high-resolution microendoscope (HRME) was developed by our collaborators at Rice University and provides greater than 1000X magnified images of the esophageal mucosa. In a single-arm, pilot study of the device in an enriched population of 60 high-risk subjects in China and the US, we used the microendoscope during routine Lugol's chromoendoscopic screening to categorize areas of abnormality (unstained areas). The sensitivity /specificity for the device seen in this study were 100% and 79%-a significant improvement over the sensitivity/specificity of Lugol's chromoendoscopy which were 97% and 52%. Thus, our presumption is that HRME can enhance the specificity (and lower the false positive rate) of Lugol's. As part of a National Cancer Institute R01 supplement (Figure 1), we have enhanced the current HRME technology by introducing an automated, ergonomic, augmented reality platform. The augmented reality platform displays, in real-time, the microscopic image colocalized with the endoscopic image, potentially allowing more targeted biopsies/treatment and increased accuracy. Our central hypothesis is that our approach can improve the efficiency and clinical impact of endoscopic screening and surveillance of ESCN by providing *in-vivo* optical biopsies comparable to standard histology. Specifically, HRME will facilitate accurate, rapid real-time endoscopic screening by non-expert clinicians. We also hypothesize the HRME will provide additional, more accurate information regarding the presence of neoplasia that will impact upon the physician's decision to obtain a mucosal biopsy or perform endoscopic therapy (endoscopic mucosal resection or ablation). This could potentially minimize the number of unnecessary biopsies and enable the physician to perform endoscopic therapy at the time of the initial examination, rather than delaying endoscopic treatment to another procedure following pathologic confirmation of the initial biopsies. We will compare (1) the current endoscopic "standard of care" (white light endoscopy with Lugol's iodine), (2) HRME with subjective, human interpretation, and (3) augmented reality HRME (software, 'machine' interpretation). The addition of (3) is the basis for our revision R01 and this amended IRB. The accuracy, efficiency, clinical impact and cost-effectiveness of each approach in the diagnosis and management of ESCN will be determined in both the Chinese and US healthcare systems. Specific endpoints: 1. Efficiency: (a) Diagnostic Yield: The number of neoplastic biopsies/total number of biopsies obtained in patients who receive biopsies. (b) 'Patients saved': Number of patients who receive no biopsies (c) Procedure time: Total procedure time in each group 2. Clinical impact: Determine potential clinical impact of HRME by determining if use of the device (with both subjective and automated read) changes the decision to perform endoscopic therapy and perform, or not perform, a mucosal biopsy when compared to LC alone. 3. Prospectively compare the performance characteristics of HRME-LC to LC for the prediction of squamous esophageal neoplasia in flat mucosa and mucosal lesions using histopathology as the gold standard. (a) Determine the sensitivity, specificity, positive and negative predictive value for the identification of neoplasia on a per biopsy and per patient analysis. 4. Determine the cost-effectiveness of HRME-LC to LC alone for the endoscopic screening and surveillance of ESCN in the US and China.

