In both groups, per standard of care, endoscopic examination will be performed using white-light endoscopy with Lugol's dye-spray. In each subject, the location of each unstained area (level, quadrant) will be recorded and digital images obtained. The endoscopist's clinical impression will be recorded for each Lugol's abnormal area and visible lesion ('nonneoplastic' vs. 'neoplastic') as well as his/her proposed plan: a. no biopsy, b. biopsy, c. endoscopic treatment/removal. In the standard-of-care arm (Group B), biopsies will be obtained of all Lugol's abnormal areas. Likewise, Group A will receive the clinician subjective HRME read + augmented reality software HRME read, sequentially, of all Lugol's unstained (abnormal) areas prior to tissue biopsy. For imaging, 1-10 ml proflavine hemisulfate (0.01%) will be sprayed on the esophageal mucosa. The HRME probe placed gently on the mucosa and the augmented reality microscopic (HRME) image displayed on the glasses, with the endoscopic image (monitor) behind it. The endoscopist will first make a subjective interpretation (neoplasia vs. no neoplasia) and plan of action (biopsy, no biopsy, treat) WITHOUT the image-analysis software. Once this qualitative ("Human") read is recorded, the image analysis software will be turned on and the software diagnosis provided in real-time. This quantitative ("Machine") read and the revised plan of action will be recorded. The HRME procedure (including Human and Machine reads) as well as standard endoscopy and biopsy time will be recorded. The research coordinators will indicate the biopsy number/location on an esophageal map diagram. The biopsies from each site will be placed in formalin per standard of care and labeled according to biopsy location (quadrant: 12, 3, 6, 9 o'clock). In all subjects, all Lugol's abnormal areas will be biopsied (to uphold the standard of care, per IRB); however, HRME "non-neoplastic" sites will be considered not tissue-biopsied for purpose of the analysis. All biopsies will be submitted for consensus diagnosis by 2 expert GI pathologists.

A schematic of the existing trial with the proposed revision is shown in Figure 2. The IRB revision is shown in RED. We anticipate that this revision will add an additional 30-60 seconds per procedure but will otherwise not change patient care.

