Endoscope Sterilization Procedures: The microendoscope is sterilized immediately after each procedure per standard endoscope accessory reprocessing guidelines. Any proflavine on the surface of the microendoscope is completely removed in the reprocessing procedure. This procedure has been approved by the FDA.

Patient Follow-Up for All Patients: All patients will recover from their procedures according to standard practice and be discharged home. To determine the safety of the HRME using topical proflavine, all pre, intra and immediate post-procedure adverse events will be recorded. Each patient will also receive a phone call from the research coordinator or co-investigator within 7 days from the study procedure to check for any post-procedure complications. In addition, prospective data will be collected on all patients at years 1,3,5 following index exam to determine whether they have progressed to a more advanced state of neoplasia.

Pathology Sample collection: Obtaining Tissue Samples from International Study Sites-Standard Operating Procedure

Biopsies from CICAMS and Jilin will be collected on H & E slides from clinical tissue blocks of all detected esophageal, high grade dysplasia and neoplasia.

The fixed biopsies will be oriented/embedded in paraffin and sectioned to facilitate comparison between histology and HRME images. Afterwards the serial sections will be routinely stained with hematoxylin and eosin for histopathologic examination.

The biopsies or resected specimens (from EMR) obtained from the examined areas will be routinely processed and interpreted by two expert GI pathologists ([name]) using standardized WHO classification criteria. Both pathologists will arrive at a consensus diagnosis which will be the official study read (gold standard).

The histopathologic diagnosis for each biopsy will be recorded on a standardized data collection form. The two central study pathologists will be reading ALL the specimens from China and the US and giving a consensus diagnosis. Image analysis will be performed comparing the actual histopathologic images to the "optical" images to develop image analysis algorithms and, potentially, image interpretations software. Rice University will be assisting in development of the image analysis algorithms for future software development.

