Separately, 10 endoscopists (6 novice and 4 expert) will be asked to interpret a selection of the HRME images. The novices will include current GI fellows at BCM and novice endoscopists on the protocol, while the expert endoscopists will be experienced endoscopists listed on the protocol. The 10 subjects will receive information about the procedures verbally as a waiver of documentation of consent is requested. Each of the subjects will first receive training using a training set, and then will be evaluated using a testing set of images. They will be asked to give a read (neoplastic or non-neoplastic) and then to provide their confidence level (high or low) for each image determination. Following the subjective HRME image read, each image will be evaluated using the automated software algorithm, with the subjective and automated reads being blinded to each other, as well as to the gold standard consensus pathology read by 2 expert GI pathologists. The subjective reads will be compared to the automated reads and the consensus pathology reads.

Subjects at the Jilin site will be asked to complete a survey addressing barriers to esophageal cancer screenings. Subjects will be asked about beliefs and attitudes surrounding screening techniques.

Section G: Sample Size/Data Analysis

G1. Sample Size

How many subjects (or specimens, or charts) will be used in this study?

Local: 300 Worldwide: 1300

Please indicate why you chose the sample size proposed:

This is an IRB revision and will NOT change our proposed sample size. Rather, in the remaining patients to be accrued, we will determine the accuracy of our revised (AR platform). Thus, the goals and sample size of the original trial will remain intact which is to compare LCE to LCE+HRME (subjective read).

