Sample Size Calculation (This has NOT changed from original IRB): The sample sizes are calculated separately for the two risk groups (650 in surveillance group and 650 in screening group). Among the surveillance group, we want to test non-inferiority in sensitivity and superiority in specificity of LCE+HRME vs. LCE alone. The standard endoscopic evaluation using LCE has high sensitivity of about 95% but with low specificity at about 65%. Based on the preliminary data, we hypothesize that LCE+HRME has the sensitivity of at least 90% level, which is similar to that of LCE, but LCE+HRME would improve the specificity to 85%. With significance level of 0.05 and 80% power, we need 223 neoplastic patients and 65 benign patients in each arm (LCE and LCE+HRME) to conclude that LCE+HRME has similar sensitivity as LCE alone and had higher specificity than LCE alone. Hence, we need 446 neoplastic patients and 130 benign patients. The sample size calculation is based on the formula in Pepe (Chapter 8, The statistical Evaluation of Medical Tests for Classification and Prediction, 2003).

According to the preliminary results, greater than 80% patients in the surveillance group would have neoplasia. We anticipate the enrollment of total 650 patients in the surveillance group to ensure the accrual of 446 neoplastic patients and 130 benign patients.

In screening group, we will study the accuracy of LCE+HRME for the diagnosis of neoplasia, and test whether the negative predictive value (NPV) of LCE+HRME is higher than LCE alone. The NPV for using LCE alone is about 95%. We hypothesize that the NPV for LCE+HRME should be at least 99% to be useful. A sample of 300 per arm would provide 82.1% power for this hypothesis with a 5% type-I error. Assuming an 8% loss to follow-up or incomplete data, we need to recruit 325 subjects per arm in the screening population.

Power Calculation (Augmented Reality HRME Revision): We anticipate having at least 400-500 subjects remaining by the time the Augmented Reality HRME revision IRB is approved and funding from the NCI obtained. With 400 patient Augmented Reality HRME data, assuming an accuracy of 83% AND 650 LC patient, assuming an accuracy of 57%, the study should have >93% power to detect a statistically significant difference with an alpha error rate of 0.05.

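### The 82.1% power for the screening NPV comparison counts all 300 patients per arm as test-negatives with known disease status, and the plan does not deliver that denominator

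*Combined protocol and SAP*

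**What the plan says.** **Power.** G1 (Sample Size) takes an NPV of about 95% for LCE alone and at least 99% for LCE+HRME, and states: "A sample of 300 per arm would provide 82.1% power for this hypothesis with a 5% type-I error". It then allows 8% for loss or incomplete data and recruits 325 per arm. G2 (Data Analysis) makes this NPV comparison the primary goal in the screening group and assigns Fisher's exact test. Neither section says whether the test is one- or two-sided.

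**Reference standard.** The reference is consensus histology: "Both pathologists will arrive at a consensus diagnosis which will be the official study read (gold standard". F2 (Procedure) specifies tissue for abnormal staining: "In the standard-of-care arm (Group B), biopsies will be obtained of all Lugol's abnormal areas". The same holds in the HRME arm, and HRME is read only on those areas. Section N says no tissue is taken purely for research. F2 also plans later follow-up, "prospective data will be collected on all patients at years 1,3,5 following index exam", to detect progression. It is not named as a reference standard for the index examination.

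**Test result.** The Lugol's reading is recorded by area: "The endoscopist's clinical impression will be recorded for each Lugol's abnormal area and visible lesion". Section D and G2 call for per-patient analysis, but the available text does not say how area readings combine into a patient result. The schematic (Figure 2) is not reproduced in the copy reviewed.

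**HRME-negative sites.** F2 has them biopsied, but these "sites will be considered not tissue-biopsied for purpose of the analysis".

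**The concern.** NPV is the proportion free of disease among patients who test negative. Its sample size is the number of test-negatives with a known answer, not the number randomised. Any patient who tests positive leaves the denominator, as does any test-negative patient without a reference diagnosis. The plan allows for neither.

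The missing positivity rule decides who is in the denominator. If a patient is LCE-positive when at least one area is called neoplastic, negatives with a biopsied area are verified, but normally stained patients are not. If any unstained area makes a patient positive, LCE-negatives have no index histology.

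This is a primary test. With the denominator open, it could be fixed after the data are seen, and a null result could be read as coming from an adequately powered comparison.

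**Working it through.** **Inputs.** From G1: NPV 0.95 and 0.99, 300 per arm, 5% type-I error, 8% loss. From G2: Fisher's exact test.

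**Step 1: reproduce 82.1%.** Put all 300 patients per arm in the NPV denominator and use the two-sided pooled z-test.

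- Standard error under the null: √(2 × 0.97 × 0.03 / 300) = 0.01393
- Standard error under the alternative: √((0.95 × 0.05 + 0.99 × 0.01) / 300) = 0.01383
- z = (0.04 − 1.96 × 0.01393) / 0.01383 = 0.918
- Power = Φ(0.918) = 82.07%

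This matches the plan. The only later adjustment is for loss: 325 × 0.92 = 299. Nothing is taken off for patients who test positive.

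**Step 2: the planned test on a realistic denominator.** Fisher power is the sum of the binomial probabilities of all outcomes with p ≤ 0.05. The two-sided p-value adds all tables no more probable than the one observed. NPVs stay at 95% and 99%.

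| Verified test-negatives per arm | Share of 300 | Fisher, two-sided | Fisher, one-sided |
|---|---|---|---|
| 300 | 100% | 79.8% | 87.6% |
| 270 | 90% | 74.1% | 83.5% |
| 250 | 83% | 69.6% | 80.1% |
| 200 | 67% | 56.3% | 68.5% |
| 150 | 50% | 39.6% | 52.1% |
| 100 | 33% | 19.4% | 30.6% |

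**Step 3: one illustrative scenario.** The plan gives no screening sensitivity, specificity, prevalence or test-negative share. As an assumption, borrow the surveillance values: LCE sensitivity 95% and specificity 65%, LCE+HRME specificity 85%.

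- An LCE NPV of 95% requires 0.05 × 0.65(1 − p) = 0.95 × 0.05p, so prevalence p = 0.0325 / 0.08 = 0.406.
- LCE test-negative share: 0.65 × 0.594 + 0.05 × 0.406 = 0.406, or 122 of 300.
- LCE+HRME true-negative share: 0.85 × 0.594 = 0.505. An NPV of 99% adds missed cases of 0.505 / 99 = 0.0051. The total is 0.510, or 153 of 300. The implied HRME sensitivity is 1 − 0.0051 / 0.406 = 98.7%.
- Fisher power with 122 versus 153: 46.7% two-sided, 50.6% one-sided.

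This assumes every test-negative is verified. Unverified normally stained patients would lower it further.

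**Step 4: HRME-negative sites.** The surveillance calculation uses 223 neoplastic patients per arm and HRME sensitivity of at least 90%. If the rule on HRME-negative sites were applied to accuracy, up to 223 × 0.10 ≈ 22 missed cases would lose the histology that shows they were missed. The clinical-efficiency endpoint in G2 needs histology from Lugol's-positive, HRME-negative patients, so the rule cannot be meant for every analysis. Its scope is not stated.

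**The case against.** **Sidedness.** The hypothesis is directional, and a one-sided Fisher test keeps at least 80% power down to about 250 verified test-negatives per arm. That stands, and the one-sided figures are shown for this reason. However, 82.1% itself matches a two-sided calculation, and 250 still requires 83% of patients to be verified negatives.

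**Follow-up as reference.** All patients are followed at years 1, 3 and 5, and the 8% allowance mentions loss to follow-up, so follow-up may have been meant to settle disease status. The text does not say so. Later progression is not index status, and follow-up would not return test-positives to the denominator.

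**Per-area NPV.** Section D lists predictive values per biopsy as well as per patient, and a per-area denominator is not capped at 300. Areas within a patient are correlated, however, and neither G1 nor the Fisher test allows for that.

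**Stronger inferences that the documents do not support.**

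- A reader might infer that power is at most 47% on the plan's own inputs. The sensitivity and specificity behind that figure belong to the surveillance group, which is sized separately, and the 41% prevalence is back-solved. It is one scenario.
- A reader might infer that LCE-alone NPV is undefined. That follows only if any unstained area counts as positive. Recording an impression per area, and the pilot's 97% sensitivity and 52% specificity for Lugol's, fit the other reading better.
- A reader might infer that HRME false negatives will be discarded. That follows only if the rule on HRME-negative sites extends to accuracy. Consensus reading of all biopsies points the other way.

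**Conclusion.** The power statement is wrong as written. It holds only if every one of 300 patients per arm is a test-negative with known disease status, and the design does not provide for that. Under the planned test, two-sided power is 79.8% at best and falls to 74%, 70%, 56% and 40% with 270, 250, 200 and 150 verified test-negatives per arm.

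The direction needs no borrowed input. The exact loss does, because the plan gives no screening test-negative share. The figures hold NPV at 95% and 99%, with equal denominators except in the illustrative scenario.

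The missing positivity rule and missing reference for normally stained patients are judged on the available text, without Figure 2. The rule on HRME-negative sites is an unstated scope, not a demonstrated error.

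**What to change.** These are changes to analysis text only. No change to biopsy practice is proposed.

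1. **Define the patient result and the denominator.** For example: LCE positive means at least one area with a recorded neoplastic impression. LCE+HRME positive means at least one area read as neoplasia on the subjective read, consistent with G1's aim to "compare LCE to LCE+HRME (subjective read"). State that NPV, sensitivity and specificity apply to patients with at least one biopsied Lugol's-abnormal area or lesion. Add that this conditioning comes after randomisation and relies on Lugol's recording being unaffected by knowledge of the arm. If any unstained area is meant to count as positive, say that LCE-alone NPV cannot be estimated from histology. Report instead the neoplasia rate among Lugol's-positive, HRME-negative patients with an exact confidence interval.
2. **Replace 82.1%** with Fisher power, sidedness stated, over a stated range of verified test-negatives per arm. As a guide, two-sided power of about 80% needs roughly 300 of these per arm. If a share f of patients qualifies in each arm, that is about 300/f evaluable patients per arm (375 at f = 0.8, 600 at f = 0.5).
3. **Limit the rule on HRME-negative sites** to diagnostic yield and biopsies saved, and use their histology in all accuracy analyses.
4. **Secondary: clinical impact.** As described, the LCE arm records one plan, so it has no change to measure. Analyse the paired change from Lugol's plan to HRME plan within the HRME-LC arm.

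**Cost.** Accuracy claims cover a narrower population, the stated screening power falls, and clinical impact loses its between-arm test. The text changes do not restore power; whether to enlarge the screening group is a separate decision for the sponsor.

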Diagnostic yield: This is defined as the proportion of all biopsies that are truly neoplastic over the total number of biopsies obtained in patients who receive biopsies. A generalized linear model for logistic regression with multiple correlated binary outcomes within each patient will be used for data analysis. In this model the binary outcome for each biopsy specimen is whether the specimen is neoplastic or non-neoplastic, and the explanatory variable is the arm (LCE+HRME vs. LCE alone) stratified by group (screening and surveillance). PROC GLIMMIX in SAS will be used because of the correlations among samples from the same patient. The model will allow for testing whether the proportion of samples classified as neoplasia differs between the 2 arms.

'Clinical efficiency': For patients that have benign disease confirmed by histology, the true proportion of patients potentially saved any biopsy using HRME (Lugol's + and HRME -) will be estimated by 95% confidence intervals (stratified by group). Proportions will be compared between groups by the chi-square test or Fisher's exact test. Procedure time in the HRME+LC arm will be compared to the LC arm by analysis of variance, stratified by group (screening and surveillance). An interaction term will also be included to determine to what extent the difference in procedure time between the 2 arms varies between the 2 risk groups.

Clinical impact: For this, the proportion of patients who had a change in the decision to perform endoscopic therapy or mucosal biopsies as a result of LCE+HRME or LCE alone, will be estimated by a 95% confidence interval. This proportion will be compared between LCE+HRME and LCE alone by the chi-square test or Fisher's exact test.

Progression rates: Five year follow-up of progression rates to more advanced pathology or esophageal cancer (EC) in the 2 arms will be conducted. Progression rates and their 95% confidence interval will be summarized and compared between LCE+HRME and LCE alone by the chi-square test or Fisher's exact test.

Safety/Adverse Events: Immediate and 48 hour adverse event (AE) rates will be compared between the LCE+HRME arm and LCE alone arm by the chi-square test or Fisher's exact test. The AE rates and their 95% confidence intervals will be summarized.

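### The rule in F2 that HRME-negative sites count as not biopsied names no endpoint; applied to the accuracy tests, it would hide HRME misses in Group A

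*Combined protocol and SAP*

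**What the plan says.** Section F2 (Procedure) sets out tissue sampling: "In all subjects, all Lugol's abnormal areas will be biopsied (to uphold the standard of care, per IRB"). The same sentence then says that HRME 'non-neoplastic' "sites will be considered not tissue-biopsied for purpose of the analysis". No endpoint is named. The next sentence reads: "All biopsies will be submitted for consensus diagnosis by 2 expert GI pathologists". Further on, F2 adds: "The two central study pathologists will be reading ALL the specimens from China and the US and giving a consensus diagnosis".

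Section D lists two efficiency endpoints that depend on whether a site counts as biopsied. Diagnostic yield is "The number of neoplastic biopsies/total number of biopsies obtained in patients who receive biopsies", and 'patients saved' is "Number of patients who receive no biopsies". Its third endpoint is sensitivity, specificity, PPV and NPV, per biopsy and per patient, "using histopathology as the gold standard".

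Section G2 makes non-inferior sensitivity with superior specificity the primary analysis in the surveillance group, and NPV the primary goal in the screening group. It cites a textbook formula and Fisher's exact test. It does not say whether the F2 rule applies to these tests. Under clinical efficiency, G2 takes patients whose disease is benign on histology and estimates "the true proportion of patients potentially saved any biopsy using HRME (Lugol's + and HRME" negative).

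**The concern.** An HRME false negative is a neoplastic site that HRME read as non-neoplastic. Those are exactly the sites that F2 treats as not biopsied. If an analyst carries the rule into the accuracy analysis, a missed neoplasia has no reference result. It then either drops out or is taken as benign.

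Only Group A has HRME reads, so the effect falls on one arm. Sensitivity in the surveillance group and NPV in the screening group are the measures meant to show whether biopsies can be skipped without missing neoplasia. Because the scope is unstated, it could also be settled after the results are known.

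**Working it through.** **Inputs.** From G1: LCE sensitivity about 95% and specificity about 65%; LCE+HRME sensitivity at least 90% and specificity 85%; 223 neoplastic and 65 benign patients per arm; significance level 0.05 and 80% power; screening NPV 95% against 99% with 300 per arm.

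**Reproducing the plan's figures.** The unpaired log-ratio formula is n = [(1−p1)/p1 + (1−p2)/p2] × (z_alpha + z_power)² / (log ratio)². With one-sided alpha 0.05, (1.645 + 0.842)² = 6.183.
- Sensitivity, both arms truly 95%, margin ratio 0.90/0.95: 0.10526 × 6.183 / 0.002923 = 222.6, so 223.
- Specificity, false-positive fractions 0.35 and 0.15: 7.5238 × 6.183 / 0.7179 = 64.8, so 65.
- NPV, two-sided comparison of 95% and 99%, 300 per arm: (0.04 − 1.96 × 0.01393) / 0.01383 = 0.918, which gives 82.1% power.

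All three agree with G1. The margin ratio and the one-sided alpha are inferred because they return 223 and 65; the documents state neither.

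**Group A under three ways of handling HRME-negative patients.** Assume each miss is a missed patient and arises at an unstained site that HRME read as non-neoplastic.
- Missed: 223 × 0.10 = 22.3. Detected: 223 − 22.3 = 200.7.
- True negatives: 65 × 0.85 = 55.25. False positives: 65 − 55.25 = 9.75.

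| HRME-negative patients | Sensitivity | Specificity | NPV |
|---|---|---|---|
| Histology kept | 200.7/223 = 90% | 55.25/65 = 85% | 55.25/77.55 = 71.2% |
| Counted benign | 200.7/200.7 = 100% | 77.55/87.3 = 88.8% | 77.55/77.55 = 100% |
| Excluded | 200.7/200.7 = 100% | 0/9.75 = 0% | 0/0, undefined |

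Here 77.55 = 55.25 + 22.3 and 87.3 = 65 + 22.3. For true sensitivity of 95% or 85%, the number missed is 223 × 0.05 = 11 or 223 × 0.15 = 33. Sensitivity still reads 100% once they are lost.

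**Non-inferiority test.** This was simulated with 200,000 repeats, control sensitivity 95%, and the inferred margin and alpha.

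| True HRME sensitivity | Passes, histology kept | Passes, misses lost |
|---|---|---|
| 85% | 0.04% | 100% |
| 90% | 5.8% | 100% |
| 95% | 79.9% | 100% |

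**Screening NPV.** The 71.2% above reflects the surveillance mix of 223 to 65 and is not a screening figure. The documents give no screening prevalence, so assume 5% to 20% and carry over sensitivity 90% and specificity 85%. NPV = 0.85(1−prev) / [0.85(1−prev) + 0.10 × prev]. This gives 99.4% at 5%, 98.7% at 10% and 97.1% at 20%. Counting HRME-negatives as benign would show 100% in each case, against the plan's 99% target.

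**The case against.** The strongest reply is that F2 speaks of biopsy status and nowhere says that histology is discarded. All tissue is taken, both pathologists read all of it, and Section D makes histology the reference for accuracy. The rule also has an obvious purpose. When every Lugol's-abnormal area is biopsied, diagnostic yield and patients saved cannot show an HRME effect unless some biopsies are treated as avoided. The clinical efficiency analysis in G2 uses the histology of Lugol's-positive, HRME-negative patients, which fits a narrow reading of the rule. Finally, the planned 85% specificity and 99% NPV need verified HRME-negatives: with those patients excluded, specificity is 0% and the superiority test fails.

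Most of this stands, and it makes the narrow reading the more likely intention. It does not close the gap. The exclusion argument rules out only exclusion. If sites treated as not biopsied are taken as benign, all three measures can still be computed, all favour the device, and no calculation fails to warn the analyst. No section states that assumption, but none rules it out.

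A reader might go further and infer that the plan does remove this histology, that HRME sensitivity and NPV are therefore inflated, and that the primary tests cannot fail. The documents do not support this. No section drops the histology from the accuracy analysis, and NPV reaches 100% only if unverified sites are also counted benign.

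**Conclusion.** The point holds as a rule of unstated scope with a serious consequence if misapplied. It does not show that the planned estimates are biased. F2 gives the only explicit instruction on HRME-negative sites, and G2 does not exempt the primary accuracy tests from it.

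If the rule reached those tests, about 22 missed patients (11 to 33 for true sensitivity of 95% to 85%) would lose their reference diagnosis, and sensitivity would read 100% whatever its true value. The distortion at 90% is 10 points, against a gap of 5 points between the planned 95% and 90%. The effect on specificity and NPV depends on whether those patients are counted benign or excluded.

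The size rests on treating each miss as a missed patient. A missed site in a patient who has another neoplastic site read positive by HRME would not change that patient's result. The pass rates also rest on the inferred margin and alpha.

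**What to change.** In F2, limit the rule to diagnostic yield and to biopsies or patients saved.

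In G2, state that sensitivity, specificity, PPV and NPV, per biopsy and per patient, use the consensus histology of every biopsied site in both arms, including sites that HRME read as non-neoplastic. Add that a patient whose only neoplastic sites were HRME-negative is a false negative.

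The cost is a few sentences. No new tissue, reading or patient is needed, because all biopsies are already taken and read. The one downside for the sponsor is that reported HRME sensitivity and NPV may be less favourable than under the literal rule.
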